Clinical research protocol

Project name: The effect and mechanism of gene variation on
neonatal hyperbilirubinemia

Leading unit: The Sixth Affiliated Hospital, Sun Yat-sen
University

Project leader: [name]

Department: Pediatrics

Research period: September 1, 2023 to December 31, 2024

Project number: EK-NHB-20230216

NCT No.: none.

Version No.: V1.0

Version Date: February 16, 2023

Abstract

object name	The effect and mechanism of gene variation on neonatal hyperbilirubinemia
goal of study	
(1) To analyze the carrying and pathogenicity of neonatal jaundice-related genes, and collect the sequencing data of jaundice-related genes (24 genes of 29 NHB-related genetic diseases) of 2000 newborns in the cooperative hospital to complete the construction of the gene database.
 
(2) To analyze the incidence of NHB-related genes, pathogenic mutations, suspected pathogenic mutations, and the carrying rate of unknown mutations in 2000 cases, and to count the distribution of high-frequency mutation sites in the population, so as to provide a scientific basis for the selection of mutation sites for large-scale neonatal hyperbilirubinemia gene screening.
 
(3) The influence of jaundice-related genes on neonatal jaundice was analyzed. The clinical data of newborns and the daily percutaneous bilirubin level were collected through the hospital hospitalization system and the " percutaneous jaundice instrument home monitoring + software doctor-patient interconnection " method to complete the construction of intelligent neonatal jaundice clinical database.
 
(4) Analyze the integrated monitoring data, statistically analyze the gene and jaundice clinical data of 2000 newborns, understand whether there is a difference in the carrying rate of related pathogenic genes in different degrees of jaundice, and explore whether there is a difference in the degree of jaundice carrying multiple and single jaundice pathogenic genes. To understand the

	correlation between gene polymorphism and clinical manifestations (phenotypic polymorphism) of neonatal hyperbilirubinemia, so as to better evaluate the effect of genes on neonatal jaundice.
research design	prospective observational study
Research period	September 2022 to December 2024
Participating	Newborns
Inclusion criteria	(1) Informed consent of parents or guardians ; (2) Age : 1-28 days, gestational age \geq 35 weeks ; (3) Birth weight \geq 2.5 kg and $<$ 4 kg.
Excluded criteria	(1) Neonatal data with unclear clinical basic information ; (2) Lack of traceability core information data ; (3) data that the test results cannot be analyzed and interpreted ; (4) Sample collection is not qualified and unwilling to cooperate with re-sampling. (5) Newborns with severe deformity and severe lethal inherited metabolic diseases
Grouping and sample size	A total of 2000 neonates were included, including 500 cases of non-significant hyperbilirubinemia (TSB / TCB $<$ 205umol / L) ; (2) 500 cases of significant hyperbilirubinemia (205umol / L \leq TSB / TCB $<$ 342umol / L) ; (3) 500 cases of severe hyperbilirubinemia (TSB / TCB \geq 342umol / L) ; 4 Extremely severe hyperbilirubinemia 500 cases (TSB / TCB \geq 428umol / L).
data collection	(1) Basic information : gender, gestational age, date of birth, birth weight, height, head circumference, mode of conception, Apgar score and parents ' information ; (2) Perinatal information : parity, parity, mode of delivery, fetal

	
membranes, amniotic fluid, placenta, umbilical cord, intrauterine distress, group B streptococcal infection, pregnancy complications such as gestational hypertension, diabetes, etc.
 
(3) Jaundice information : blood types of parents and newborns, feeding methods, monitoring jaundice values, jaundice treatment methods and related test results ;
 
(4) Test results : Collect genetic analysis results, notes, etc.

Statistical processing	IBM-SPSS 26.0 statistical software was used to analyze the test results. Logistic multivariate regression analysis was used to evaluate the correlation between genotype and clinical phenotype, and mediating variables were used to analyze the correlation between gene-gene interaction and genotype-phenotype.
abbreviation	neonatal hyperbilirubinemia, NHB; total serum bilirubin, TSB; transcutaneous bilirubin, TCB; Principal Investigator, PI.

1. Research background

Neonatal disease screening is one of the most effective public health initiatives, which has been carried out for more than 60 years. Since the single screening of phenylketonuria (PKU) in 1961, with the improvement of screening technology, it has developed into a screening of more than 50 diseases including endocrine system diseases (congenital hypothyroidism, congenital adrenal hyperplasia), hemoglobin disease, infectious diseases, cystic fibrosis, and congenital metabolic diseases. The incidence of birth defects is related to genetic and environmental factors. Among the patients with birth defects diagnosed by etiology, 94.4 % are caused by chromosomal abnormalities and genetic variations. Because most patients have a genetic basis, early screening and diagnosis have important scientific value and social significance for the prevention and control of these diseases.

At present, neonatal disease screening methods are diverse, including : neonatal metabolic disease screening (hypothyroidism, phenylketonuria, adrenocortical hyperplasia, G-6-PD deficiency and metabolic disease tandem mass spectrometry screening), hearing screening, fundus screening, cardiac ultrasound, etc. However, although the above-mentioned routine screening techniques play an important role in the prevention and control of birth defects, there are still obvious deficiencies : 1) There are many interference factors, such as susceptibility to sample quality, blood collection time, gestational age, birth weight and other factors, and false positive or false negative are more likely to occur, which brings a greater psychological burden to the children 's families. At the same time, biochemical tests, tandem mass spectrometry, urinary organic acids and other methods are needed to assist diagnosis after recall ; 2) For children with positive screening, further gene sequencing is needed to confirm the diagnosis and typing, and further develop an accurate treatment plan. During this period, the diagnosis may be delayed for 1-2 months. For children with severe illness, the damage to the nervous system is often irreversible, and even the treatment is not timely and life-threatening during the detection period ; 3) Traditional methods can only make a preliminary diagnosis, and can not be clearly classified, and more birth defects of

different types, treatment options vary. At present, the mainstream technology of neonatal screening has the problems of limited methods, long time for diagnosis, easy delay in disease treatment, and direct impact on the prognosis of children. Therefore, efficient and accurate screening techniques need to be developed and applied.

The development of genomics technology has pushed the diagnosis and prevention of hereditary birth defects to a new height. With the rapid development of gene sequencing technology and the deepening of medical genetics research, more and more genetic screening and related clinical studies of genetic diseases caused by genetic variation have been widely carried out at home and abroad, highlighting the broad prospects of neonatal disease screening and diagnosis based on gene detection in early diagnosis and early prevention of birth defects.

Neonatal hyperbilirubinemia, also known as neonatal jaundice, is the most common clinical manifestation of newborns. It has many causes and is difficult to diagnose. Genetic factors are one of the common causes of metabolic-related jaundice. According to statistics, about 60 % to 80 % of newborns can have varying degrees of jaundice, and severe cases can cause a series of body damage, including nerve, hearing, cardiovascular and kidney function, and even cause death. Within 7-27 days after birth, the incidence of death in children due to neonatal jaundice is about 107.1 / 100,000, ranking ninth in the global causes of late neonatal death. The common causes of neonatal jaundice include neonatal ABO hemolysis, RH hemolysis, neonatal sepsis, and congenital hypothyroidism. Genetic factors play an important role in the metabolism of bilirubin. Hyperbilirubinemia is mainly caused by bilirubin metabolism or circulatory disorders. Clinically, it can be manifested as high unconjugated hyperbilirubinemia and hyperconjugated hyperbilirubinemia. At present, the gold standard for the detection of neonatal jaundice is to use venous blood to detect bilirubin as the main laboratory examination method. In addition, it also includes micro-blood bilirubin meter detection, percutaneous bilirubin measurement and visual inspection. However, such detection does not have high diagnostic sensitivity and specificity and cannot determine whether it is jaundice caused by genetic factors. Genetic metabolism-related jaundice has great

individual differences in age of onset and clinical manifestations. Even if the same pathogenic gene mutation is carried out, the clinical phenotype can be different. Therefore, the application of genetic testing in this type of disease can improve the early diagnosis of the disease. Genetic testing of children without jaundice or hospitalized jaundice can obtain the proportion of genetic factors and their genotypes in children with jaundice, so as to continuously improve the efficiency of disease diagnosis.

However, previous studies have focused on the role of one or two specific genes in patients with hyperbilirubinemia. For example, a number of studies have shown that the UGT1A1 gene hotspot c.211G > A polymorphism is a risk factor for NHB, and is closely related to the severity of jaundice, and can aggravate the symptoms of breast milk jaundice, glucose-6-phosphate dehydrogenase deficiency, hereditary spherocytosis, and hemolytic jaundice caused by congenital erythropoietic anemia. Yang et al. showed that the c.211G > A locus was a risk factor for severe hyperbilirubinemia in patients with glucose-6-phosphate dehydrogenase deficiency. Watchko et al. showed that a single G6PD gene mutation or UGT1A1 gene mutation only caused mild jaundice, but the coexistence of the two mutations may cause severe NHB or even nuclear jaundice. Up to now, there is no literature report on the study of gene polymorphism and clinical manifestation polymorphism of jaundice in large data population.

The transcutaneous jaundice instrument (YSJ-20) has obtained the ' People 's Republic of China Class II Medical Device Registration Certificate '. It can accurately, quickly, safely and non-invasively detect the current bilirubin level of the newborn through the skin appearance. It is portable, easy to operate, and has a low threshold for use. It is very suitable for family members to monitor the level of neonatal jaundice at home.

In summary, this study intends to collect heel peripheral blood samples from 2000 newborns [including 500 non-significant hyperbilirubinemia newborns, 500 significant hyperbilirubinemia newborns, 500 severe hyperbilirubinemia newborns and 500 extremely severe hyperbilirubinemia newborns]. The gene capture sequencing

technology containing 24 genes of neonatal common hereditary jaundice genes was used to detect and collect the clinical data of these 2000 newborns. At the same time, the percutaneous jaundice meter (YSJ-20) was used to monitor the daily jaundice at home. According to the analysis results of gene detection and clinical data of jaundice in 2000 children, the carrying rate of pathogenic genes of common hereditary jaundice in neonates was studied, and the carrying rate of pathogenic genes in different degrees of jaundice was understood. Whether there is a difference in the degree of jaundice with multiple and single jaundice pathogenic genes, and the correlation between gene polymorphism and clinical manifestations (phenotypic polymorphism) of neonatal hyperbilirubinemia were analyzed.

2. Research objective

(1) To analyze the carrying and pathogenicity of neonatal jaundice-related genes, and to collect the sequencing data of jaundice-related genes (24 genes of 29 NHB-related genetic diseases) of 2000 newborns in the cooperative hospital, and to complete the construction of the gene database.

(2) To analyze the incidence of NHB-related genes, pathogenic mutations, suspected pathogenic mutations, and the carrying rate of unknown mutations in 2000 cases, and to count the distribution of high-frequency variation sites in the population, so as to provide a scientific basis for the selection of mutation sites for large-scale neonatal hyperbilirubinemia gene screening.

(3) The influence of jaundice-related genes on neonatal jaundice was analyzed. The clinical data of newborns and the daily percutaneous bilirubin level were collected through the hospital hospitalization system and the " percutaneous jaundice instrument home monitoring + software doctor-patient interconnection " method, and the construction of intelligent neonatal jaundice clinical database was completed.

(4) Analyze the integrated monitoring data, statistically analyze the gene and jaundice data of 2000 newborns, understand whether there is a difference in the carrying rate of related pathogenic genes in different degrees of jaundice, and explore whether there is a difference in the degree of jaundice carrying multiple and single jaundice pathogenic genes. To understand the correlation between gene polymorphism and clinical manifestations (phenotypic polymorphism) of neonatal hyperbilirubinemia, thereby increasing the accuracy of genetic diagnosis.

3. Research Design

This study is a prospective observational study. Three drops of heel peripheral blood samples were collected from 2000 newborns, and 24 genes of 29 NHB-related genetic diseases were analyzed. All dry blood spot samples that met the inclusion criteria could be included in the genetic analysis. At the same time, the clinical data of these 2000 newborns were collected, and the daily jaundice monitoring at home was performed using the percutaneous jaundice meter (YSJ-20). The data were synchronized to the mobile phone jaundice follow-up doctor assistant small program for storage statistics. The family members can view the jaundice risk level and obtain free doctor consultation in the small program.

The purpose of this study is to study the carrying rate of pathogenic genes of common hereditary jaundice diseases in newborns, to understand whether there is a difference in the carrying rate of pathogenic genes in different degrees of jaundice, to explore whether there is a difference in the degree of jaundice carrying multiple and single jaundice pathogenic genes, and to analyze the correlation between gene polymorphism and clinical manifestations (phenotypic polymorphism) of neonatal hyperbilirubinemia, so as to evaluate the feasibility of jaundice gene screening program in the detection of jaundice-related genetic metabolic diseases.

Based on the 'Classification Criteria and Guidelines for Genetic Variation (2017)', the variation pathogenicity of genetic testing is divided into five categories : known pathogenic, possible pathogenic, unclear significance, possible benign and benign. In this study, known pathogenic and possible pathogenic are classified as positive results. The pathogenicity of the mutation site is mainly based on the pathogenic mutation database and the latest literature reports.

The classification criteria of jaundice were based on the American Academy of Pediatrics (AAP) 2022 edition of neonatal hyperbilirubinemia management guidelines for gestational age ≥ 35 weeks and the latest version of 2023 guidelines to interpret the management of neonatal hyperbilirubinemia-the diagnosis and intervention criteria of neonatal hyperbilirubinemia in the American Academy of Pediatrics and multi-national clinical management guidelines. The 2000 neonates were divided into 500 cases of non-

significant hyperbilirubinemia ($TSB / TCB < 205\text{umol} / \text{L}$), 500 cases of significant hyperbilirubinemia ($205\text{umol} / \text{L} \leq TSB / TCB < 342\text{umol/L}$), 500 cases of severe hyperbilirubinemia ($TSB/TCB \geq 342\text{umol/L}$) and 500 cases of extremely severe hyperbilirubinemia ($TSB/TCB \geq 428\text{umol} / \text{L}$).

4. Inclusion criteria

- (1) Informed consent of parents or guardians ;
- (2) Age : 1-28 days, gestational age ≥ 35 weeks ;
- (3) Birth weight ≥ 2.5 kg and < 4 kg.

5. Excluded criteria

- (1) Neonatal data with unclear clinical basic information ;
- (2) Lack of traceability core information data ;
- (3) data that the test results cannot be analyzed and interpreted ;
- (4) Sample collection is not qualified and unwilling to cooperate with re-sampling.
- (5) Newborns with severe deformity and severe lethal inherited metabolic diseases

6. termination criteria

- (1) The family members of the newborn included in the study requested termination at any time ;
- (2) The relevant management departments require termination.

7. outcome index

Through the comprehensive analysis of genetic variation information and jaundice clinical data, the carrying rate of pathogenic genes of common hereditary jaundice diseases in newborns was counted, and the difference of carrying rate of pathogenic genes in different degrees of jaundice was understood. To explore whether there is a difference in the degree of jaundice carrying multiple and single jaundice pathogenic genes, and to analyze the correlation between gene polymorphism and clinical manifestations (phenotypic polymorphism) of neonatal hyperbilirubinemia.

8. Grouping and sample size

This study is a prospective observational study. According to the positive mutation rate of NHB-related genes in neonatal hyperbilirubinemia, P is about 30 %, the test level α

= 0.05 and the allowable error $\delta = 2 \%$, n (sample size) = ($U\alpha / \delta$) $2 * p * (1 - P) \approx$ 2000 cases. A total of 2000 neonates were included, including 500 cases of non-significant hyperbilirubinemia ($TSB / TCB < 205\text{umol} / L$) ; (2) 500 cases of significant hyperbilirubinemia ($205\text{umol} / L \leq TSB / TCB < 342\text{umol} / L$) ; (3) 500 cases of severe hyperbilirubinemia ($TSB / TCB \geq 342\text{umol} / L$) ; (4) Extremely severe hyperbilirubinemia 500 cases ($TSB / TCB \geq 428\text{umol} / L$) .

9. Recruiting

This study will recruit subjects in the outpatient and inpatient departments of pediatrics, neonatology, and obstetrics in the South China Neonatal Genetic Screening Alliance (including cooperation units of 49 hospitals).

10. Clinical evaluation index

- (1) The carrying rate, positive rate, negative rate and high-frequency mutation sites of common NHB-related gene mutation sites in neonates ;
- (2) The difference in the carrying rate of NHB-related pathogenic genes in neonates with different degrees of jaundice ;
- (3) The difference of jaundice degree between carrying multiple and single jaundice pathogenic genes ;
- (4) Gene-gene interaction and genotype-phenotype correlation.

11. Methods

11.1 gene sequencing

A total of 24 genes were included in 29 NHB-related genetic diseases, including bilirubin metabolic disorders, congenital bile acid synthesis or transport disorders, red blood cell metabolic defects, lipid metabolic abnormalities, and metal metabolic abnormalities. The detected genes included ABCB11, ABCB4, ABCC2, ABCD3, ACOX2, AKR1D1, AMACR, ATP7B, ATP8B1, CYP7B1, G6PD, GBA, HBB, HSD3B7, JAG1, NOTCH2, NPC1, NPC2, NR1H4, SLC10A1, SLC25A13, SMPD1, TJP2 and UGT1A1. Gene and genetic disease related information refer to OMIM and Orphanet database.

Target gene sequence capture and library construction. Three drops of heel peripheral

blood were collected by filter paper, and genomic DNA was extracted by magnetic bead method. The target gene sequence was captured by multiplex PCR amplification method, covering all exon regions and adjacent intron regions ($\pm 50\text{bp}$) of the target gene. A total of 900 amplicons were designed for 24 genes and completed in two amplification systems. The target sequence library was obtained after amplification-purification-re-amplification-re-purification. The library was quantified using a Qubit[®] 3.0 fluorescence quantitative instrument (Thermo Fisher Scientific), and the library length was determined using an Aglient 2100 biological analyzer (Agilent) (228-378 bp).

High-throughput sequencing and bioinformatics analysis. The library was diluted, added sequencing primers, and sequenced on the Illumina NextSeq 550 platform (PE150). The effective sequencing data were aligned to the human reference genome (Human _ B37) by BWA (Burrows-Wheeler Aligner) software. GATK (Genome Analysis ToolKit) was used to analyze the variation information, and ANNOVAR software was used to annotate the variation, including the annotation information of dbSNP database, Thousand Human Genome Project and other existing databases. The annotation content covers population frequency, mutation type, function prediction (SIFT, Polyphen2, Mutation Taster, etc.), HGMD, Clinvar and other pathogenic classification information. Based on the ' Classification Criteria and Guidelines for Genetic Variation (2017) ', the pathogenic interpretation of genetic variation was divided into five categories : ' pathogenic ', ' possible pathogenic ', ' unclear significance ', ' possible benign ' and ' benign '. Among them, ' pathogenic ', ' possible pathogenic ' and ' unclear significance ' were included in the statistics of test results.

Validation of positive loci. For children with autosomal recessive double heterozygosity and children with autosomal dominant single heterozygosity, Sanger sequencing was used to verify the loci of their parents.

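### The only stated basis for choosing screening sites is how often they occur; no per-site comparison across severity classes is planned or linked to that choice

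*Combined protocol and SAP*

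**What the plan says.** Objective (2) in section 2 asks for the carrying rates of the pathogenicity classes among the 2000 infants. It then asks "to count the distribution of high-frequency variation sites in the population, so as to provide a scientific basis for the selection of mutation sites", the intended use being large-scale gene screening for hyperbilirubinemia. The Abstract repeats this under goal (2) ("count the distribution of high-frequency mutation sites in the population"). No other text ties an analysis to the choice of sites.

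Section 10, index (1), treats sites in the same way: "The carrying rate, positive rate, negative rate and high-frequency mutation sites of common NHB-related gene mutation sites in neonates". Section 12 says that the carrying rate of sites is counted and plans no further site-level analysis by name.

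Severity enters elsewhere:
- Objective (4), index (2) and section 12 compare carrying rates across degrees of jaundice, but for pathogenic genes. Objective (4) gives the purpose of its analyses as more accurate genetic diagnosis.
- Index (4) and section 12 plan a genotype-phenotype analysis by logistic regression, without saying whether the unit is a site, a gene or a combined genotype.
- Section 3 links the analyses as a whole to the feasibility of the screening programme.

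Section 8 fixes the sample by severity: "A total of 2000 neonates were included, including 500 cases of non-significant hyperbilirubinemia", with 500 in each of the other three classes.

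**The concern.** How often a site occurs does not show whether its carriers become more jaundiced. One gene can hold both severity-related and neutral sites, so a difference found for a gene does not say which of its sites to screen. If those who later build the panel have only the outputs of objective (2), they cannot tell the two kinds apart, although the data to do so will have been collected.

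A second problem concerns the count itself. The four classes are filled to equal size by design, so a frequency pooled over them reflects the 500:500:500:500 allocation and not the mix of severity among newborns. Objective (2) nevertheless describes it as a distribution in the population.

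**Working it through.** **1. The plan's own sample size.** Section 8 states "P is about 30 %, the test level α" = 0.05 and an allowable error of 2%. The formula is n = (U/δ)² × P × (1 − P).
- Two-sided: (1.96/0.02)² × 0.30 × 0.70 = 2016.8, which agrees with about 2000.
- A one-sided value gives 1420 and does not agree.
- The 95% half-width at P = 30% is 1.96 × √(0.21/2000) = 2.0 points for all infants, and 1.96 × √(0.21/500) = 4.0 points within one class.

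The size is therefore set for the precision of one pooled rate. The documents give no site-level rates, no effect by severity and no number of candidate sites.

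**2. What a pooled count hides.** All rates here are assumed.

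| | Non-significant | Significant | Severe | Extremely severe | Pooled | Carriers in 2000 |
|---|---|---|---|---|---|---|
| Site A | 4% | 4% | 4% | 4% | 4.0% | 80 |
| Site B | 0.5% | 1% | 2% | 3% | 1.625% | about 33 |

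Contrast: severe and extremely severe combined (1000 infants) versus non-significant (500).
- Site A: likelihood ratio 4/4 = 1.0; odds ratio 1.0.
- Site B: combined rate (2% + 3%)/2 = 2.5%. Likelihood ratio 2.5/0.5 = 5.0. Odds ratio (0.025/0.975)/(0.005/0.995) = 5.1.
- For extremely severe versus non-significant alone, B gives a likelihood ratio of 6.0 and an odds ratio of 6.2.

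The pooled count shows A as about 2.5 times as common as B (4.0/1.625) and nothing else.

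**3. Population frequency.** A frequency in newborns weights the class rates by the true severity mix, which the documents do not give. For site A the mix does not matter. For site B the result could lie anywhere from 0.5% to 3%; the 1.625% follows only from equal weights.

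**4. What the planned sample can show per site.** Rates are assumed, tests are two-sided at 0.05, and a Bonferroni factor of 24 (the number of genes) stands in for the unknown number of sites.

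| Contrast | Power, one site | Power, 24-fold Bonferroni |
|---|---|---|
| 6% vs 2%, 1000 vs 1000 (normal approximation) | 99.6% | 93% |
| 3% vs 1%, 1000 vs 1000 (normal approximation) | 89% | 55% |
| 2.5% vs 0.5%, 1000 vs 500 (Fisher's exact) | 85% | 38% |

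Moderately frequent enriched sites can be assessed; rare ones often cannot.

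**5. Why an interval should not exclude a site.** With 8 carriers in 1000 against 0 in 500, the exact 95% interval for the odds ratio starts at 0.86. With 10 in 1000 against 1 in 500, the odds ratio is 5.0 and the interval runs from 0.71 to 219. A rule requiring the interval to exclude 1 would drop both, and these are the kind of rare, enriched sites that the table is meant to reveal.

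**The case against.** A reader might infer that the plan will choose sites by frequency alone, so that common uninformative sites displace rarer informative ones. The documents do not support that. They contain no ranking, threshold or selection rule; objective (2) offers the counts as a basis for a later choice.

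Frequency is also not the only filter. Objective (2) breaks rates down by pathogenicity class, section 3 counts only known and possibly pathogenic variants as positive, and section 18 speaks of pathogenic sites of high frequency. This stands, with two limits. Section 3 grades pathogenicity mainly from databases and literature, not from this study's bilirubin data, and section 11.1 also brings variants of unclear significance into the statistics. Section 1 itself notes that the same pathogenic mutation can produce different phenotypes.

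The genotype-phenotype regression might already be a site-level severity analysis. Section 1 uses the word polymorphism for a single site, and objective (4) correlates gene polymorphism with clinical manifestations. This reading is possible, but the unit is not defined and the result is not linked to site selection. The link in section 3 concerns the programme's feasibility and gives no basis for choosing among sites.

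Finally, the screening target is ambiguous. Objective (2) and section 18 refer to hyperbilirubinemia; section 3 refers to jaundice-related genetic metabolic diseases. For the second aim, a pathogenic site may matter without raising bilirubin. This is a good reason to keep pathogenicity class as a criterion in its own right and not to rank by odds ratio alone.

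**Conclusion.** The point holds as a gap in specification. The plan offers only frequencies as the basis for site selection and neither defines a per-site severity comparison nor connects one to that choice. As written, objective (2) and index (1) cannot separate severity-related sites from neutral ones, and their pooled figure is not a population frequency. That conclusion follows from the text and the fixed allocation and needs no assumed rate.

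The size does rest on assumption. The contrast between 1.6% with an odds ratio of 5.1 and 4.0% with an odds ratio of 1.0 shows that frequency and severity association can point in opposite directions. It does not show that they will do so here. The change is worth making because the severity-stratified data will already exist.

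**What to change.** In objective (2) (and the matching Abstract goal), index (1) and section 12:

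1. For each candidate site, report the pathogenicity class and the carrier frequency in each of the four severity classes with an exact 95% CI.
2. Report the odds ratio for severe and extremely severe combined versus non-significant, with an exact CI. Name the multiplicity method and the set of sites to which it applies.
3. State that frequency, pathogenicity class and severity association together form the basis for site selection.
4. State that no site is excluded because its interval includes no difference, and that rare sites with wide intervals are labelled inconclusive.
5. Say whether the logistic regression in section 12 uses sites as its unit, and do not describe the pooled count as a population frequency.

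The cost is SAP wording and one extra table from data already being collected, with no new infants or measurements. The downside is that intervals for rare sites will be wide and many of those sites will remain inconclusive.
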